9.4.4.3. PK Summaries

PK concentrations (including voriconazole concentrations in induced sputum) will be summarised and plotted over time. All PK parameters will also be summarised.

Further statistical analysis of other PK parameters and induced sputum concentrations may be performed. Full detail will be provided in the SAP.

9.5. Interim Analyses

No formal interim analyses are planned for this study. Details of interim safety data reviews to be performed are described in Section 6.6.

9.6. Data Monitoring Committee (DMC)

No data monitoring committee is planned for this study.

10. Supporting Documentation and Operational Considerations

10.1. Appendix 1: Regulatory, Ethical, and Study Oversight Considerations

10.1.1. Regulatory and Ethical Considerations

- This study will be conducted in accordance with the protocol and with the following:
 - Consensus ethical principles derived from international guidelines including the Declaration of Helsinki and Council for International Organizations of Medical Sciences (CIOMS) International Ethical Guidelines
 - o Applicable ICH Good Clinical Practice (GCP) Guidelines
 - Applicable laws and regulations
 - 20 July 2017 EMEA/CHMP/SWP/28367/07 Rev. 1 Committee for Medicinal Products for Human Use (CHMP) Guideline on strategies to identify and mitigate risks for first-in-human and early clinical trials with investigational medicinal products
 - 21 July 2011 EMEA/CHMP/EWP/192217/2009 Committee for Medicinal Products for Human Use (CHMP) Guideline on bioanalytical method validation
 - London, 20 January 2010 Doc. Ref.: CPMP/QWP/EWP/1401/98 Rev. 1 Guideline on the investigation of bioequivalence"
 - https://www.gov.uk/guidance/managing-clinical-trials-during-coronavirus-covid-19 guidance.
- The protocol, protocol amendments, ICF, Investigator Brochure, and other relevant documents (e.g., advertisements) must be submitted to an IEC by the investigator and reviewed and approved by the IEC before the study is initiated.
- Any substantial amendments to the protocol will require IEC approval before implementation of changes made to the study design, except for changes necessary to eliminate an immediate hazard to study participants.
- The investigator will be responsible for the following:
 - Providing written summaries of the status of the study to the IEC annually or more frequently in accordance with the requirements, policies, and procedures established by the IEC
 - Notifying the IEC of SAEs or other significant safety findings as required by IEC procedures
 - Providing oversight of the conduct of the study at the site and adherence to requirements of 21 CFR, ICH guidelines, the IEC, European regulation 536/2014 for clinical studies (if applicable), and all other applicable local regulations.

10.1.2. Financial Disclosure

Investigators and sub-investigators will provide the sponsor with sufficient, accurate financial information as requested to allow the sponsor to submit complete and accurate financial certification or disclosure statements to the appropriate regulatory authorities. Investigators are responsible for providing information on financial interests during the course of the study and for 1 year after completion of the study.

10.1.3. Informed Consent Process

- The investigator or his/her representative will explain the nature of the study to the subject and answer all questions regarding the study.
- Subjects must be informed that their participation is voluntary. Subjects or their legally authorised representative will be required to sign a statement of informed consent that meets the requirements of 21 CFR 50, local regulations, ICH guidelines, General Data Protection Regulation (GDPR), and the IEC or study centre.
- The medical record must include a statement that written informed consent was obtained before the subject performed any study procedures and the date the written consent was obtained. The authorised person obtaining the informed consent must also sign the ICF.
- Subjects must be re-consented to the most current version of the ICF(s) during their participation in the study.
- An original signed ICF(s) must be provided to the subject or the subject's legally authorised representative.

Subjects who are rescreened are required to sign a new ICF.

10.1.4. Data Protection

- Subjects will be assigned a unique identifier by the sponsor. Any subject records or datasets that are transferred to the sponsor will contain the identifier only; subject names or any information which would make the subject identifiable will not be transferred.
- The subject must be informed that his/her personal study-related data will be used by the sponsor in accordance with local data protection law. The level of disclosure must also be explained to the subject who will be required to give consent for their data to be used as described in the informed consent
- The subject must be informed that his/her medical records may be examined by Clinical Quality Assurance auditors or other authorised personnel appointed by

the sponsor, by appropriate IEC members, and by inspectors from regulatory authorities.

10.1.5. Committees Structure

Data reviews during the study will be performed by the Safety Advisory Committee (SAC). See section 6.6 for details of the committee structure.

10.1.6. Dissemination of Clinical Study Data

A clinical study summary report will be provided to the appropriate IEC and results uploaded to EudraCT within one year of the end of the clinical study.

10.1.7. Data Quality Assurance

- All subject data relating to the study will be recorded on an electronic CRF unless transmitted to the sponsor or designee electronically (e.g., laboratory data). The investigator is responsible for verifying that data entries are accurate and correct by electronically signing the CRF.
- The investigator must maintain accurate documentation (source data) that supports the information entered in the CRF.
- The investigator must permit study-related monitoring, audits, IEC review, and regulatory agency inspections and provide direct access to source data documents.
- Monitoring details describing strategy (e.g., risk-based initiatives in operations and quality such as Risk Management and Mitigation Strategies and Analytical Risk-Based Monitoring), methods, responsibilities and requirements, including handling of noncompliance issues and monitoring techniques (central, remote, or on-site monitoring) are provided in the Monitoring Plan.
- The sponsor or designee is responsible for the data management of this study including quality checking of the data.
- The sponsor assumes accountability for actions delegated to other individuals (e.g., Contract Research Organizations).
- Study monitors will perform ongoing source data verification to confirm that data
 entered into the CRF by authorised site personnel are accurate, complete, and
 verifiable from source documents; that the safety and rights of subjects are being
 protected; and that the study is being conducted in accordance with the currently
 approved protocol and any other study agreements, ICH GCP, and all applicable
 regulatory requirements.
- Records and documents, including signed ICFs, pertaining to the conduct of this study must be retained by the investigator for 15 years after study completion

unless local regulations or institutional policies require a longer retention period. No records may be destroyed during the retention period without the written approval of the sponsor. No records may be transferred to another location or party without written notification to the sponsor.

10.1.8. Source Documents

- Source documents provide evidence for the existence of the subject and substantiate the integrity of the data collected. Source documents are filed at the investigator's site.
- Data reported on the CRF or entered in the eCRF that are transcribed from source documents must be consistent with the source documents or the discrepancies must be explained. The investigator may need to request previous medical records or transfer records, depending on the study. Also, current medical records must be available.
- Definition of what constitutes source data can be found in source data verification agreement (or equivalent).

10.1.9. Study and Site Start and Closure

The study start date is the date on which the clinical study will be open for recruitment of subjects.

The first act of recruitment is the first site open and will be the study start date.

The sponsor reserves the right to close the study site or terminate the study at any time for any reason at the sole discretion of the sponsor. Study sites will be closed upon study completion. A study site is considered closed when all required documents and study supplies have been collected and a study-site closure visit has been performed.

The investigator may initiate study-site closure at any time, provided there is reasonable cause and sufficient notice is given in advance of the intended termination.

Reasons for the early closure of a study site by the sponsor or investigator may include but are not limited to:

- Failure of the investigator to comply with the protocol, the requirements of the IEC or local health authorities, the sponsor's procedures, or GCP guidelines
- Inadequate recruitment of subjects by the investigator
- Discontinuation of further study intervention development

If the study is prematurely terminated or suspended, the sponsor shall promptly inform the Investigators, the IECs, the regulatory authorities, and any contract research organisation(s) used in the study of the reason for termination or suspension, as specified by the applicable regulatory requirements. The Investigator shall promptly inform the subject and should assure appropriate subject therapy and/or follow-up.

10.1.10. Publication Policy

- The results of this study may be published or presented at scientific meetings. If this is foreseen, the investigator agrees to submit all manuscripts or abstracts to the sponsor before submission. This allows the sponsor to protect proprietary information and to provide comments.
- The sponsor will comply with the requirements for publication of study results. In accordance with standard editorial and ethical practice, the sponsor will generally support publication of multicenter studies only in their entirety and not as individual site data. In this case, a coordinating investigator will be designated by mutual agreement.
- Authorship will be determined by mutual agreement and in line with International Committee of Medical Journal Editors authorship requirements

10.2. Appendix 2: Clinical Laboratory Tests

Haematology	Clinical Chemistry	Virology	Urinalysis	Urine Drugs of Abuse
Basophils Eosinophils Haematocrit (Packed Cell Volume- PCV) Haemoglobin Lymphocytes Mean Cell Haemoglobin (MCH) Mean Cell Haemoglobin Concentration (MCHC) Mean Cell Volume (MCV) Monocytes Neutrophils Platelet Count Red Blood Cell (RBC) Count White Blood Cell (WBC) Count	Alanine Aminotransferase (ALT) Albumin Alkaline Phosphatase Aspartate Aminotransferase (AST) Bicarbonate Bilirubin (Total) Bilirubin (Direct) (only if Total is elevated) Calcium Chloride Creatine Kinase (CK) Creatinine Follicle Stimulating Hormone (FSH; may be performed for postmenopausal female subjects to confirm post menopausal status at discretion of investigator) hCG (all female subjects) Gamma Glutamyl Transferase (GGT) Glucose Glucose (Fasting) Lactate dehydrogenase (LDH) Potassium Phosphate (Inorganic) Protein (Total) Sodium Urea	Hepatitis B Surface Antigen Hepatitis B Surface Antibody Hepatitis B Core Antibody Hepatitis C Virus Antibody Hepatitis C Virus RNA HIV Antibody Test for SARS-COV-2 (RT-PCR)	Bilirubin Blood Glucose hCG (all female subjects) Ketones Leukocytes Nitrites pH Protein Specific gravity Urobilinogen If urinalysis is positive for protein, blood, nitrite and/or leukocytes, a microscopic examination (for red blood cells, white blood cells, bacteria, casts, and epithelial cells) will be performed.	Amphetamines Barbiturates Benzodiazepines Cocaine Cotinine Marijuana/Cannabis Methadone Methamphetamine/ Ecstasy Morphine/ Opiates Phencyclidine Tricyclic Antidepressants

10.3. Appendix 3: Adverse Events: Definitions and Procedures for Recording, Evaluating, Follow-up, and Reporting

10.3.1. Definition of AE

AE Definition

- An AE is any untoward medical occurrence in a patient or clinical study subject, temporally associated with the use of IMP, whether or not considered related to the study IMP.
- NOTE: An AE can therefore be any unfavorable and unintended sign (including an abnormal laboratory finding), symptom, or disease (new or exacerbated) temporally associated with the use of study intervention.

Events Meeting the AE Definition

- Any abnormal laboratory test results (hematology, clinical chemistry, or urinalysis) or other safety assessments (e.g., ECG, radiological scans, vital signs measurements), including those that worsen from baseline, considered clinically significant in the medical and scientific judgment of the investigator (i.e., not related to progression of underlying disease).
- Exacerbation of a chronic or intermittent pre-existing condition including either an increase in frequency and/or intensity of the condition.
- New conditions detected or diagnosed after IMP administration even though it may have been present before the start of the study.
- Signs, symptoms, or the clinical seguelae of a suspected drug-drug interaction.
- Signs, symptoms, or the clinical sequelae of a suspected overdose of either study intervention or a concomitant medication. Overdose per se will not be reported as an AE/SAE unless it is an intentional overdose taken with possible suicidal/self-harming intent. Such overdoses should be reported regardless of sequelae.

Events NOT Meeting the AE Definition

- Any clinically significant abnormal laboratory findings or other abnormal safety assessments which are associated with the underlying disease, unless judged by the investigator to be more severe than expected for the subject's condition.
- The disease/disorder being studied or expected progression, signs, or symptoms of the disease/disorder being studied, unless more severe than expected for the subject's condition.

- Medical or surgical procedure (e.g., endoscopy, appendectomy): the condition that leads to the procedure is the AE.
- Situations in which an untoward medical occurrence did not occur (social and/or convenience admission to a hospital).
- Anticipated day-to-day fluctuations of pre-existing disease(s) or condition(s) present or detected at the start of the study that do not worsen.

10.3.2. Definition of SAE

If an event is not an AE per definition above, then it cannot be an SAE even if serious conditions are met (e.g., hospitalisation for signs/symptoms of the disease under study, death due to progression of disease).

A SAE is defined as any untoward medical occurrence that, at any dose:

a. Results in death

b. Is life-threatening

The term 'life-threatening' in the definition of 'serious' refers to an event in which the subject was at risk of death at the time of the event. It does not refer to an event, which hypothetically might have caused death, if it were more severe.

c. Requires inpatient hospitalisation or prolongation of existing hospitalisation

- In general, hospitalisation signifies that the subject has been detained (usually involving at least an overnight stay) at the hospital or emergency ward for observation and/or treatment that would not have been appropriate in the physician's office or outpatient setting. Complications that occur during hospitalisation are AEs. If a complication prolongs hospitalisation or fulfills any other serious criteria, the event is serious. When in doubt as to whether "hospitalisation" occurred or was necessary, the AE should be considered serious.
- Hospitalisation for elective treatment of a pre-existing condition that did not worsen from baseline is not considered an AE.

d. Results in persistent disability/incapacity

- The term disability means a substantial disruption of a person's ability to conduct normal life functions.
- This definition is not intended to include experiences of relatively minor medical significance such as uncomplicated headache, nausea, vomiting, diarrhea, influenza, and accidental trauma (e.g., sprained ankle) which may interfere with or prevent everyday life functions but do not constitute a substantial disruption.

e. Is a congenital anomaly/birth defect

f. Other situations:

- Medical or scientific judgment should be exercised in deciding whether SAE
 reporting is appropriate in other situations such as important medical events that
 may not be immediately life-threatening or result in death or hospitalisation but
 may jeopardise the subject or may require medical or surgical intervention to
 prevent one of the other outcomes listed in the above definition. These events
 should usually be considered serious.
- Examples of such events include invasive or malignant cancers, intensive treatment in an emergency room or at home for allergic bronchospasm, blood dyscrasias or convulsions that do not result in hospitalisation, or development of drug dependency or drug abuse.

10.3.3. Recording and Follow-Up of AE and/or SAE

AE and SAE Recording

- When an AE/SAE occurs, it is the responsibility of the investigator to review all documentation (e.g., hospital progress notes, laboratory reports, and diagnostics reports) related to the event.
- The investigator will then record all relevant AE/SAE information in the CRF.
- It is **not** acceptable for the investigator to send photocopies of the subject's medical records to the Sponsor in lieu of completion of the AE/SAE CRF page.
- There may be instances when copies of medical records for certain cases are requested by the Sponsor. In this case, all subject identifiers, with the exception of the subject number, will be redacted on the copies of the medical records before submission to the Sponsor.
- The investigator will attempt to establish a diagnosis of the event based on signs, symptoms, and/or other clinical information. Whenever possible, the diagnosis (not the individual signs/symptoms) will be documented as the AE/SAE.

Assessment of Intensity

The investigator will make an assessment of intensity for each AE and SAE reported during the study and assign it to 1 of the following categories:

- Mild: An event that is easily tolerated by the subject, causing minimal discomfort and not interfering with everyday activities.
- Moderate: An event that causes sufficient discomfort and interferes with normal everyday activities.
- Severe: An event that prevents normal everyday activities. An AE that is assessed as severe should not be confused with a SAE. Severe is a category

utilised for rating the intensity of an event; and both AEs and SAEs can be assessed as severe.

An event is defined as 'serious' when it meets at least 1 of the predefined outcomes as described in the definition of an SAE, NOT when it is rated as severe.

Assessment of Causality

- The investigator is obligated to assess the relationship between study intervention and each occurrence of each AE/SAE. The relationship should be classified as follows:
 - Not related: a causal relationship between the study IMP and the AE is not a reasonable possibility
 - Related: a causal relationship between the study IMP and the AE is a reasonable possibility, and there are no other obvious causes for the AE.
- A "reasonable possibility" of a relationship conveys that there are facts, evidence, and/or arguments to suggest a causal relationship, rather than a relationship cannot be ruled out.
- The investigator will use clinical judgment to determine the relationship.
- Alternative causes, such as underlying disease(s), concomitant therapy, and other risk factors, as well as the temporal relationship of the event to study intervention administration will be considered and investigated.
- The investigator will also consult the Investigator's Brochure (IB) and/or Product Information, for marketed products, in his/her assessment.
- For each AE/SAE, the investigator **must** document in the medical notes that he/she has reviewed the AE/SAE and has provided an assessment of causality.
- There may be situations in which an SAE has occurred and the investigator has
 minimal information to include in the initial report to the Sponsor. However, it is
 very important that the investigator always make an assessment of causality for
 every event before the initial transmission of the SAE data to the Sponsor.
- The investigator may change his/her opinion of causality in light of follow-up information and send a SAE follow-up report with the updated causality assessment.
- The causality assessment is one of the criteria used when determining regulatory reporting requirements.

Follow-up of AEs and SAEs

- The investigator is obligated to perform or arrange for the conduct of supplemental measurements and/or evaluations as medically indicated or as requested by the Sponsor to elucidate the nature and/or causality of the AE or SAE as fully as possible. This may include additional laboratory tests or investigations, histopathological examinations, or consultation with other health care professionals.
- If a subject dies during participation in the study or during a recognised followup period, the investigator will provide the Sponsor with a copy of any post-mortem findings including histopathology.
- New or updated information will be recorded in the originally completed CRF.
- The investigator will submit any updated SAE data to the Sponsor within 24 hours of receipt of the information.

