6.6.4. Criteria for Safety Advisory Committee

Dose levels for each cohort (Parts 1 and 2) and Part 3 will be decided during the SAC meetings.

The SAC may also agree for additional subjects to be included for an intermediate dose level if warranted or may agree to reduce or increase (see Section 4.3) the dose. Any decision to investigate an intermediate or reduced dose level will be fully documented.

The decision to proceed to the next higher dose level will be based on safety and tolerability data. The following data (minimum of 24 hours post-dose) are required for dose escalation decisions:

- Adverse events
- Vital signs (including systolic and diastolic blood pressure, pulse rate, respiratory rate and pulse oximetry)
- Safety laboratory (including clinical chemistry, haematology and urinalysis)
- ECG
- Physical examinations
- Spirometry assessments (including FEV₁, forced vital capacity [FVC], peak expiratory flow rate [PEFR] and FEV₁/FVC)

If, following review by the SAC it is deemed acceptable to continue dose escalation above the maximum dose described in this protocol (40 mg ZP-059), a substantial amendment with relevant data will be submitted for approval to the regulatory authorities and ethics committee (EC).

Dose escalation will not occur if:

 One or more subjects in a cohort experiences a serious adverse event (SAE) related to IMP.

٥r

 Two or more subjects in a cohort experiences severe non-serious AEs related to IMP.

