6.6.5. Stopping Criteria

6.6.5.1. Part 1, Part 2 and Part 3

All parts of the study will be halted, if any of the following criteria are met:

- The occurrence of an SAE considered related to the IMP administration in 1 subject.
- The occurrence of severe, non-serious AEs considered related to the IMP administration in 2 subjects at the same dose level (Part 1 and Part 2).

 The occurrence of severe, non-serious AEs considered related to the IMP administration in 2 subjects receiving the same treatment (i.e. 2 subjects receiving ZP-059 or 2 subjects receiving oral voriconazole) in Part 3.

Relatedness will be determined by the investigator (see Section 10.3.3). If the study is halted, a temporary halt will be submitted to the Medicines and Healthcare products Regulatory Agency (MHRA) and EC in the form of a substantial amendment. The study will not be resumed until a further substantial amendment to resume the study is submitted and approved by MHRA and EC.

7. Discontinuation of Investigational Medicinal Product and Subject Discontinuation/Withdrawal

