#### 7.13.1.1 Treatment-emergent Adverse Events

A treatment-emergent adverse event (TEAE) is defined as an AE that started on or after the start of the administration of study treatment. If adverse event dates are incomplete and it is not clear whether the adverse event was treatment-emergent, it will be assumed to be treatment-emergent.

In Part 3 of the study, AEs are treatment emergent and accountable to the Period 1 treatment if they started on or after the start of the administration of study treatment in Period 1 up to the first administration of study treatment in Period 2. For Period 2, AEs are treatment emergent and accountable to the Period 2 treatment if they started on or after the start of the administration of study treatment in Period 2 up to the end of the follow-up period.

A treatment related TEAE is defined as a TEAE that is related to the study treatment. If the TEAE has a missing relationship it is assumed to be related to the study treatment for analysis purposes.

A summary table will present the following:

- TEAEs (events and subjects).
- Serious TEAEs (events and subjects).
- Serious study treatment related TEAEs (events and subjects).
- TEAEs by severity (mild/moderate/severe) (events and subjects).
- TEAEs by relationship to study treatment (events and subjects).
- TEAEs leading to withdrawal from study (subjects only).
- TEAEs leading to discontinuation of study treatment (subjects only).
- Study treatment related TEAEs leading to discontinuation of study treatment (subjects only).
- TEAEs leading to death (subjects only).

In the above summaries, if a subject experienced more than one TEAE, the subject will be counted once using the most related event for the "by relationship to study

treatment" and "related to study treatment" summaries, and by the worst severity for the "by severity" summary.

The following tables will be presented:

- TEAEs by SOC and PT.
  - If a subject experienced more than one TEAE assigned to the same treatment, the subject will be counted once for each SOC and once for each PT within that treatment.
- TEAEs by PT.
  - If a subject experienced more than one TEAE assigned to the same treatment, the subject will be counted once for each PT within that treatment.
- TEAEs by SOC, PT and severity.
  - If a subject experienced more than one TEAE assigned to the same treatment, the subject will be counted once for each SOC and once for each PT at the worst severity/CTC grade within that treatment.

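### The two causality categories in Protocol 10.3.3 are not complements, so a severe or serious event with both a reasonable drug link and another obvious cause may drop out of the related-only safety rules

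*Protocol*

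**What the plan says.** Protocol 10.3.3 (Assessment of Causality) obliges the investigator to assess every AE and SAE and gives two categories:

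- "Not related: a causal relationship between the study IMP and the AE is not a reasonable possibility".
- *Related*: a causal relationship "is a reasonable possibility, and there are no other obvious causes for the AE".

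It sets the bar for a reasonable possibility: the phrase "conveys that there are facts, evidence, and/or arguments to suggest a causal relationship, rather than a relationship cannot be ruled out". On method it says "The investigator will use clinical judgment to determine the relationship", and "Alternative causes, such as underlying disease(s), concomitant therapy, and other risk factors, as well as the temporal relationship of the event to study intervention administration" are to be considered and investigated.

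The numeric safety rules count only related events. Under 6.6.4 escalation is barred by one related SAE in a cohort, or if "Two or more subjects in a cohort experiences severe non-serious AEs related to IMP". Under 6.6.5 all parts halt after one related SAE, after related severe non-serious AEs in two subjects at the same dose level (Parts 1 and 2), or after such AEs in two subjects on the same treatment (Part 3). That section adds "Relatedness will be determined by the investigator" and points to 10.3.3.

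SAP 7.13.1.1 tabulates TEAEs as related or unrelated. It treats a missing relationship as related for analysis purposes.

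**The concern.** A two-category scale should place every event. Here *Related* carries a second condition that has no counterpart in *Not related*, so one kind of event has no place. The SAP rule for a missing relationship does not help once the investigator has ticked a box.

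The gap lies close to the risk this product is watched for. Protocol 2.3.3 calls bronchoconstriction an expected reaction to inhaled therapy. Parts 2 and 3 enrol only asthmatic subjects and include sputum induction, which 2.3.5 recognises can itself provoke bronchoconstriction. The thresholds are one or two subjects, so one or two classifications can decide whether a numeric rule is met. The documents do not say how those classifications should go.

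**Working it through.** **Step 1. Cross the two conditions in 10.3.3.**

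| Reasonable possibility? | Other obvious cause? | Category |
|---|---|---|
| No | No | *Not related* |
| No | Yes | *Not related* |
| Yes | No | *Related* |
| Yes | Yes | none |

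Three of the four combinations are classified and one is not.

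**Step 2. Look for another route.** 10.3.3 requires a causality assessment for every event, and for SAEs before the first transmission to the sponsor. The SAP tables have two columns. The SAP's missing-relationship rule covers only a blank field and only the final analysis. SAP section 6 says its statistical group produces no outputs for the dose reviews. Nothing supplies the missing category.

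**Step 3. Can the empty cell be filled in practice?** Yes, although the documents do not say how often. Protocol 2.3.3 gives an argument for a reasonable possibility. 10.3.3 itself names underlying disease as an alternative cause. Induction takes place on Day 7 in Part 2 (pre-dose, 3 h and 6 h). In Part 3 it takes place in each period, first at 2 h after dosing.

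**Step 4. Which rules are touched for asthmatic subjects?**

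| Rule | Part 2 | Part 3 |
|---|---|---|
| Escalation bar (6.6.4) | yes | no escalation step |
| Halting rule (6.6.5) | yes | yes |
| Related-TEAE tables (SAP 7.13.1.1) | yes | yes |

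The first two count only SAEs or severe events. A mild or moderate non-serious event never counts there, whatever its causality.

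**Step 5. Illustrate the size.** The plan gives no event rate or operating characteristic, so there is no figure to reproduce. Let p be the assumed chance that a subject has a severe (or serious) event with a reasonable possibility of causation. Let q be the assumed share of those recorded *Related*. With independent subjects, P(rule met) = P(X ≥ r), where X ~ Binomial(n, p·q).

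For n = 6, r = 2, p = 0.2:
- q = 1: 1 − 0.8⁶ − 6(0.2)(0.8⁵) = 0.345
- q = 0.5: 1 − 0.9⁶ − 6(0.1)(0.9⁵) = 0.114
- q = 0.25: 1 − 0.95⁶ − 6(0.05)(0.95⁵) = 0.033

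| Rule | p | q = 1 | q = 0.5 | q = 0.25 |
|---|---|---|---|---|
| ≥2 severe, Part 2 cohort, n = 6 | 0.1 | 0.114 | 0.033 | 0.009 |
| same | 0.2 | 0.345 | 0.114 | 0.033 |
| same | 0.3 | 0.580 | 0.224 | 0.069 |
| ≥2 severe, minimum escalation data, n = 4 | 0.2 | 0.181 | 0.052 | 0.014 |
| ≥1 SAE, n = 6 | 0.2 | 0.738 | 0.469 | 0.265 |
| ≥2 severe on ZP-059, Part 3, n = 16 | 0.2 | 0.859 | 0.485 | 0.189 |

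These values show direction only; p and q are assumptions.

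**The case against.** The strongest reply is that the definition does not work alone. The Safety Advisory Committee receives all AEs and spirometry with no causality filter (6.6.4). Escalation needs every party's agreement and clear support from the safety data (6.6.1, 6.6.2). Moderate or severe bronchospasm is an AESI whatever its cause (8.12.7). Several withdrawal criteria in 7.1 do not depend on causality. TEAEs are also tabulated by SOC and PT regardless of relationship, and spirometry is summarised. All of this stands and limits the harm. But these safeguards work through discretion, act on the individual subject or report after the fact. None replaces the numeric triggers, and none fills the empty cell.

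A reader might also infer more than the documents support:

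- *That an asthmatic's bronchospasm can never be* Related*, or that all 34 planned asthmatic subjects (18 + 16) have an alternative cause for any respiratory event.* Having stable asthma does not make asthma an obvious cause of a given event. Timing must be weighed and the call is one of clinical judgment, so *Related* remains available, notably for an event soon after inhalation. Induction cannot explain an event before the first Part 3 induction at 2 h, or on Days 1 to 6 of Part 2.
- *That the text sends such events to* Not related*.* Read literally, they fail that definition too. The text leaves them unplaced, and the direction of any bias depends on the investigator.
- *That every formal safety decision rests on this word.* Only the numeric rules, the related-event tables and the causality element of regulatory reporting do.
- *That the other period's voriconazole is a competing cause in Part 3.* Oral voriconazole is the reference IMP. An earlier dose raises the question of which treatment, not of IMP versus something else.

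**Conclusion.** The point stands as a defect in a stated rule: mandatory classification with two categories that leave one combination unassigned. Its practical reach is narrow but important. It concerns severe or serious events, chiefly airway events in Parts 2 and 3, for which the investigator sees both a reasonable link to IMP and another obvious cause. Whether such an event counts towards the numeric rules is then a matter of individual interpretation. The related-TEAE tables are exposed in the same way, at any severity.

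The logical gap follows from the text alone. How much it matters depends on how often such events occur and how they are recorded, and the documents give neither. For a cohort of six with p from 0.1 to 0.3, recording half of these events as *Related* rather than all lowers the chance of meeting the two-subject rule from 0.114–0.580 to 0.033–0.224. The extra condition is not needed to prevent over-attribution: reasonable possibility already demands positive evidence, and alternative causes are already weighed in judging it.

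**What to change.** In Protocol 10.3.3, delete the part of the *Related* definition that follows the comma in "is a reasonable possibility, and there are no other obvious causes for the AE". The two categories then become reasonable possibility and no reasonable possibility, and every event has a place. Keep the bullet on alternative causes and timing as part of judging whether a reasonable possibility exists. Add one sentence stating that a co-existing cause, such as asthma or a recent sputum induction, does not by itself make an event *Not related*. Repeat it in the CRF completion guidance.

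No threshold in 6.6.4 or 6.6.5 changes, and the SAP's related/unrelated tables and missing-relationship rule can stay. The cost is one deleted clause, one added sentence and a CRF note. The downside is that somewhat more events may be called related, so a numeric rule could be met sooner.
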